10 DATA MANAGEMENT AND QUALITY ASSURANCE

The Investigator will maintain accurate source documentation including patient medical records, laboratory reports, ECG strips, and patient diaries.

Investigative site qualified personnel will enter patient data into an EDC system. The analysis data sets will be a combination of these data and data from other sources.

Clinical data management will be performed in accordance with applicable standards and data cleaning procedures to ensure the integrity of the data (e.g., removing errors and inconsistencies in the data). AEs will be coded using the Medical Dictionary for Regulatory Activities (MedDRA). Concomitant medications will be coded using the World Health Organization (WHO) Drug Dictionary.

After database lock, each study site will receive information about all of their site-specific eCRF data as entered into the EDC system for the study, including full discrepancy and audit history. Additionally, a copy of study data from all sites will be created and sent to the Sponsor for storage. The CRO will maintain a duplicate copy for its records. In all cases, patient initials will not be collected or transmitted to the Sponsor.

For detailed instruction on data entry procedures and timelines, please refer to the eCRF Completion Guidelines.

11 ETHICAL, REGULATORY, AND STUDY MANAGEMENT CONSIDERATIONS

11.1 Regulatory and Ethical Conduct of the Study

The study will be performed in accordance with the ethical principles that have their origin in the Declaration of Helsinki, International Council for Harmonisation (ICH) Good Clinical Practice (GCP), and all applicable regulations. **For France sites only:** Any reference to the patient's legally authorized representative/legal guardian in [Section 11](#) is not applicable, as per the request from the French Central Ethics Committee (CEC).

11.2 Independent Ethics Committee or Institutional Review Board

Federal regulations and ICH guidelines require that approval be obtained from an Institutional Review Board (IRB)/IEC before participation of human patients in research studies. Before study onset, the protocol, informed consent, advertisements to be used for the recruitment of study patients, and any other written information regarding this study intended to be provided to the patient or the patient's legally authorized representative must be approved by the IRB/IEC. Documentation of all IRB/IEC approvals will be maintained by the site and will be available for review by the Sponsor or its designee.

All IRB/IEC approvals should be signed by the IRB/IEC chairman or designee and must identify the IRB/IEC name and address, the clinical protocol by title or protocol number or both, and the date approval or a favorable opinion was granted.

The Investigator is responsible for obtaining continued review of the clinical research as specified by the IRB/IEC, at intervals not exceeding 1 year. The Investigator must supply the Sponsor or its designee with written documentation of continued review of the clinical research.

11.3 Patient Information and Consent

Informed consent in compliance with IRB/IEC and local regulations shall be obtained from each patient or their legally authorized representative before performing any study procedures and will be documented with a signed IRB/IEC approved ICF. Before enrollment, each prospective patient or his or her legally authorized representative will be given a full explanation of the study and be allowed to read the approved ICF. Once the Investigator is assured that the patient/legally authorized representative understands the implications of participating in the study, the patient/legally authorized representative will be asked to give consent to participate in the study and sign the ICF. The process for obtaining consent has to be documented at the institution.

If the ICF is revised during the course of the study, all patients on-study, including those in follow-up, must sign the revised form, unless otherwise indicated by the IRB/IEC (local or global, as applicable). In such cases, the reason for not re-consenting the patient should be documented.

11.4 Confidentiality

All laboratory specimens, evaluation forms, reports, and other records will be identified in a manner designed to maintain patient confidentiality. All records will be kept in a secure storage area with limited access. Clinical information will not be released without the written permission of the patient (or the patient's legal guardian), except as necessary for monitoring and auditing by the Sponsor, its designee, regulatory authorities, or the IRB/IEC.

The Investigator and other study staff may not disclose or use for any purpose other than performance of the study any data, record, or other unpublished, confidential information disclosed to those individuals for the purpose of the study. Prior written agreement from the Sponsor or its designee must be obtained for the disclosure of any said confidential information to other parties.

11.5 Financial Disclosure and Obligations

Investigators are required to provide financial disclosure information to allow the Sponsor to submit the complete and accurate certification or disclosure statements as required under 21 Code of Federal Regulations (CFR) 54 and local regulations. In addition, the Investigator must promptly update this information if any relevant changes occur during the course of the investigation and for 1 year following the completion of the study.

11.6 Serious Adverse Events Report Requirements

The Sponsor will ensure that all relevant safety information (SAEs and SUSARs) is reported to the FDA and competent authorities of European Member States, and to the IRB/IEC, in accordance with current legislation.

11.7 Study Conduct

The Investigator will conduct all aspects of this study in accordance with the principles of the current version of ICH E6 as well as all national, state, and local laws and regulations. Study personnel involved in conducting this study will be qualified by education training and experience to perform their respective tasks. Study information from this protocol will be posted on publicly available clinical study registers before enrollment of patients begins.

11.8 Protocol Amendments

Any change in the study plan requires a protocol amendment. All amendments to the protocol must be reviewed and approved following the same process as the original protocol before the amended protocol can be implemented. The Investigator will inform the governing IRB/IEC of all protocol amendments issued by the Sponsor in accordance with established IRB/IEC procedure. Only protocol amendments intended to eliminate an apparent immediate hazard to patient(s) may be implemented immediately, i.e., without IRB/IEC approval, but the circumstances of the change must be documented and submitted to the IRB/IEC.

11.9 Monitoring of the Study

All aspects of the study will be carefully monitored by the Sponsor or designee for compliance with GCP and applicable government regulations.

Investigators and institutions involved in the study will permit study-related monitoring, audits, IRB/IEC review, and regulatory inspections by providing direct access to all study records. In the event of an audit/inspection, the Investigator agrees to allow the Sponsor, representatives of the Sponsor, or a regulatory agency access to all study records.

The Investigator should promptly notify the Sponsor and the CRO of any inspections scheduled by any regulatory authorities and promptly forward copies of any inspection reports received to the Sponsor.

11.10 Records Retention

Essential documents should be retained for at least 15 years from the completion of the study (last patient last visit) or until at least 2 years after the last approval of a marketing application in an ICH region or until there are no pending or contemplated marketing applications in an ICH region or at least 2 years have elapsed since the formal discontinuation of clinical development of the investigational study drug. However, these documents should be retained for a longer period if required by the applicable regulatory requirements or by an agreement with the Sponsor. It is the responsibility of the Sponsor to inform the Investigator/institution as to when these documents no longer need to be retained.

11.11 Publications

Following completion of the study, the results from the study may be reported publicly by making any oral public presentation and/or submitting or presenting a manuscript, abstract, or other materials relating to the Study at scientific meetings and/or to a publisher, reviewer, or other outside person in scientific journals (“Publication”), provided, however, that Publication of the results from an individual site shall not be made before the first multi-site Publication by Sponsor. The Sponsor shall coordinate the drafting, editing, authorship, and other activities related to study Publication and shall mutually agree with the Investigator(s) on the number, medium, forum, and timing for Publication. The Sponsor shall solicit input regarding contents of the Publication from all Investigators and in consultation with all sites. The Sponsor acknowledges the right of the Investigator(s) to publish the results of this study after the entire study has completed, but also reserves the right to a window to review the Publication for regulatory compliance as well as for protection of its intellectual property. In particular, the Sponsor may request to remove the Sponsor’s confidential information and suspend Publication for a certain period of time to protect the Sponsor’s intellectual property interest, as further set forth in the Clinical Trial Agreement with the clinical study site(s) and Investigator(s).

## Glossary of Abbreviations

Glossary of Abbreviations:	
AE	Adverse event
AESI	Adverse event of special interest
BMI	Body mass index
BOR	Best overall response
C1D1	Cycle 1 Day 1
CI	Confidence interval
■■■■■	■■■■■
CR	Complete response
CRF	Case report form
CSR	Clinical study report
CTCAE	Common Terminology Criteria for Adverse Events
DCR	Disease control rate
DESC	Dose Escalation Steering Committee
DLBCL	Diffuse Large B-Cell Lymphoma
DLT	Dose limiting toxicity
DoR	Duration of response
ECG	Electrocardiogram
ECOG	Eastern Cooperative Oncology Group
EOS	End of Study
EOT	End of Treatment
IP	Investigational product
IRC	Independent Review Committee
IV	Intravenous
MCL	Mantle Cell Lymphoma
MedDRA	Medical Dictionary for Regulatory Activities
NCI	National Cancer Institute
NE	Not evaluable
ORR	Overall response rate
OS	Overall survival
PD	Progressive disease
PFS	Progression-free survival
PK	Pharmacokinetic
PR	Partial response

PT	Preferred term
QTc	Corrected QT interval
RP2D	Recommended Phase 2 Dose
SAE	Serious adverse event
SAP	Statistical analysis plan
SD	Stable disease
SOC	System organ class
SPD	Sum of Product of the Perpendicular Diameters
std	Standard deviation
TEAE	Treatment-emergent adverse event
TANT	Tumor-associated non tumor
WHODRUG DD	World Health Organization Drug Dictionary

## 1 Introduction

This statistical analysis plan (SAP) describes the statistical methods to be used during the reporting and analysis of data collected under ADC Therapeutics Protocol ADCT-402-103.

This SAP should be read in conjunction with the study protocol and case report form (CRF). This version of the plan has been developed using the Protocol Amendment 5 dated 31 August 2021.

Since this study was early terminated due to lack of efficacy singnal. The current number of patients will be reduced in Phase 1 dose escalation , Phase 1 does expansion, and Phase 2.

## **2 Study Objectives**

### **2.1 Primary Objectives**

#### **Phase 1:**

- To characterize the safety and tolerability of loncastuximab tesirine in combination with ibrutinib, and to identify the MTD/recommended dose and schedule for future studies

#### **Phase 2:**

- To evaluate the efficacy of loncastuximab tesirine given at every cycle in combination with ibrutinib in patients with relapsed or refractory DLBCL

[figure not shown]
### **2.2 Secondary Objectives**

#### **Phase 1:**

- To evaluate the antitumor effect of the combination of loncastuximab tesirine with ibrutinib
- To characterize the pharmacokinetic (PK) profile of loncastuximab tesirine when given in combination with ibrutinib
- To evaluate the immunogenicity of loncastuximab tesirine when given in combination with ibrutinib

#### **Phase 2:**

- To further evaluate the safety and efficacy of loncastuximab tesirine in combination with ibrutinib in non-GCB DLBCL, GCB DLBCL, all DLBCL and MCL patients
- To further evaluate the PK profile and immunogenicity of loncastuximab tesirine when given in combination with ibrutinib
- To evaluate the impact of the combination on patient-reported outcomes (PROs)

### 3 Study Objectives and Endpoints

Objectives	Endpoints
Primary	
Secondary	
Phase 1:	
Phase 1:
 
Overall response rate (ORR) according to the 2014 Lugano classification as determined by Investigator. ORR defined as the proportion of patients with a BOR of CR or partial response (PR) Phase 1 and Phase 2
 
Phase 1 and Phase 2:
 
Duration of response (DOR) defined as the time from the documentation of first tumor response to disease progression or death, in the non-GCB DLBCL, GCB DLBCL, all DLBCL, and MCL patients
 
Relapse-free survival (RFS) defined as the time from the documentation of CR to disease progression or death in the non-GCB DLBCL, GCB DLBCL, all DLBCL, and MCL patients
 
Progression-free survival (PFS) defined as the time between start of treatment and the first documentation of progression, or death in the non-GCB DLBCL, GCB DLBCL, all DLBCL, and MCL patients
 
Overall survival (OS) defined as the time between the start of treatment and death from any cause in the non-GCB DLBCL, GCB DLBCL, all DLBCL, and MCL patients
 
Concentrations and PK parameters of loncastuximab tesirine (total antibody, pyrrolobenzodiazepine (PBD)-conjugated antibody, and unconjugated cytotoxin SG3199) in the non-GCB DLBCL, GCB DLBCL, all DLBCL, and MCL patients
 
Anti-drug antibody (ADA) titers and, if applicable, neutralizing activity to loncastuximab tesirine in the non-GCB DLBCL, GCB DLBCL, all DLBCL, and MCL patients

Phase 2:	
Phase 2:
 
ORR according to the 2014 Lugano classification in the non-GCB DLBCL, GCB DLBCL, all DLBCL, and MCL patients. ORR defined as the proportion of patients with a BOR of CR or PR for all treated patients.
 
ORR is determined by IRC and/or Investigator.
 
CRR according to the 2014 Lugano classification(Cheson et al., 2014) as determined by IRC and/or Investigator in the non-GCB DLBCL, GCB DLBCL, all DLBCL, and MCL patients
 
CRR according to the 2014 Lugano classification(Cheson et al., 2014) as determined by investigator in the non-GCB DLBCL patient
 
Frequency and severity of AEs and SAEs in the non-GCB DLBCL, GCB DLBCL, all DLBCL, and MCL patients
 
Change from baseline of safety laboratory values, vital signs, ECOG performance status, and 12-lead ECGs in the non-GCB DLBCL, GCB DLBCL, all DLBCL, and MCL patients
 
Change from baseline in PROs as measured by the European Organization for Research and Treatment of Cancer (EORTC) QLQ-C30, LymS of FACT4-y, and EQ-5D-5L, in the non-GCB DLBCL, GCB DLBCL, all DLBCL, and MCL patients

## 4 Study Design

This is a Phase 1/2 open-label single-arm combination study, with a dose escalation Phase 1 followed by Phase 2. The study will enroll approximately 136 patients.

### Phase 1:

A standard 3+3 dose escalation design will be used. The DLT Period will be the first 21 days of ibrutinib treatment. The dose escalation cohort will receive loncastuximab tesirine for 2 cycles with concurrent ibrutinib (concomitant therapy) and may then continue ibrutinib therapy up to 1 year. An additional dose level of 75 µg/kg loncastuximab tesirine will be explored and evaluated during this phase of the study.

A Dose Escalation Steering Committee (DESC) composed of study investigators and ADC Therapeutics personnel will be responsible for decisions concerning dose escalation. At the discretion of the DESC, enrollment may be expanded to further evaluate safety and efficacy at any dose level that has completed the 3+3 dose escalation cohort with no more than 1 DLT in 6 patients. Additional patients may be added only if there is at least 1 patient with documented PR or CR.

No more than 10 patients in each of the 2 treatment cohorts (GCB DLBCL and MCL) can be treated at the expanded enrollment portion of Phase 1, and up to 20 patients will be treated in the non-GCB DLBCL cohort. This will allow the trial to enroll approximately 40 patients among the 3 expanded cohorts.

When the maximum tolerated dose (MTD) or Recommended Phase 2 Dose (RP2D) is defined there will be an efficacy and safety evaluation made by the Sponsor in consultation with investigators to determine benefit risk of the combination therapy. Once MTD or RP2D is determined and if there is a  $\geq 10\%$  improvement observed in CRR or ORR in any of the treatment cohorts in all DLBCL, non-GCB, GCB, or MCL when compared to the loncastuximab tesirine monotherapy, along with an acceptable safety profile, then Phase 2 of the study will commence.

Patients who have a response of PR or stable disease (SD) at the 14-week disease assessment may receive 2 additional doses of loncastuximab tesirine given 4 weeks apart (C5D1 and C6D1). Ibrutinib will be administered orally at 560 mg once daily continuously during all cycles containing ibrutinib.

### Phase 2:

Once the dose level of loncastuximab tesirine has been defined, the Phase 2 portion of the study will enroll in 3 separate cohorts: non-GCB DLBCL, GCB DLBCL, and MCL.

Each of the cohorts will be treated at the RP2D dose of loncastuximab tesirine determined in Phase 1 and ibrutinib. An IRC will be used in all cohorts to evaluate the response to the combination therapy.

Loncastuximab tesirine will be administered on C1D1 and C2D1. Patients who have a response of CR, PR, and SD at later disease assessments (Week 14 and Week 30) will receive additional doses of loncastuximab tesirine on C5D1, C6D1, C9D1, and C10D1. Ibrutinib will be administrated orally at 560 mg once daily continuously during all cycles. In the non-GCB DLBCL cohort, a Simon's 2-stage design will be used with an interim analysis for futility on the first 22 patients. If  $\geq 6$  patients achieve CR, this cohort will proceed to complete full enrollment. Enrollment will continue during the interim analysis; however, further enrollment in this cohort will be halted if futility is confirmed.

As of the data cutoff April 21, 2021, the interim analysis for non-GCB and GCB DLBCL cohorts was performed and the futility on non-GCB DLBCL was not met.

Subsequent to the interim analysis showing the potential of every cycle dosing of loncastuximab tesirine (see Protocol Section 2.2), the following will be performed:

- RP2D will be re-determined by DESC.
- Enrollment of the non-GCB DLBCL cohort treated with the combination of loncastuximab tesirine administered at an intermittent dose schedule and daily ibrutinib will be closed. GCB and MCL will complete the enrollment target set forth in the initial phase 2 design and remain under the initial treatment schedule.
- A new Phase 2 cohort of approximately 100 R/R DLBCL patients (with at least 40 patients each of GCB and non-GCB) will be introduced at the re-determined RP2D of loncastuximab tesirine administered in every cycle in combination with ibrutinib po daily given.

Patients will receive loncastuximab tesirine Q3W on Day 1 of first 2 cycles, followed by Q4W on Day 1 of every subsequent cycles. Ibrutinib will be administered at 560 mg po daily for first two cycles, then a dose reduction to 420 mg po daily for subsequent cycles.

A two-stage design with futility monitoring will be used for this new Phase 2 cohort. In the first stage, 60 patients will be accrued. If there are 20 or fewer CRs in these 60 patients, this cohort will be stopped. Otherwise, 40 additional patients will be accrued for a total of 100.

The study will include a Screening Period (of up to 28 days), a Treatment Period (cycles of 3 to 4 weeks), and a Follow-up Period (approximately every 12-week visits for up to 2 years after treatment discontinuation). On March 3, 2022, ADC Therapeutics announced to discontinue the study. The new Phase 2 cohort will be not enrolled.

## 4.1 Sample Size Consideration

There will be 136 patients for the entire study.

### Phase 1:

47 patients will be treated with the combination of loncastuximab tesirine and ibrutinib.

## **Phase 2:**

89 patients will be treated during Phase 2 study.

The 89 patients will be treated with the combination of loncastuximab tesirine and ibrutinib in three different cohorts:

- 49 Non-GCB DLBCL was to enroll and treated interim data analysis for futility. The study will close with approximately 48 patients.
- GCB DLBCL cohort will enroll approximately 30 patients, and
- MCL cohort will enroll approximately 10 patients

Approximately 100 R/R DLBCL patients with at least 40 patients each for GCB and non-GCB will be accrued to the new treatment cohort where loncastuximab tesirine is given at every cycle with ibrutinib po daily.

### **Phase 2 Sample Size Justification for the non-GCB DLBCL Cohort Where Loncastuximab Tesirine is Given Intermittently in Combination with Ibrutinib**

The primary hypothesis is that the CRR based on central review for patients treated with loncastuximab tesirine and ibrutinib is significantly greater than 20% (i.e.,  $H_0: p \leq 0.2$  vs.  $H_a: p > 0.2$ ). This hypothesis will be tested at type I error of 0.05 (two sided).

Simon's 2-stage design (Simon, 1989) will be used for Phase 2 non-GCB DLBCL cohort. The null hypothesis that the true CRR is 0.2 will be tested against a one-sided alternative. In the first stage, 22 patients will be accrued. If there are 5 or fewer CRs in these 22 patients, this cohort will be stopped. Otherwise, 44 additional patients will be accrued for a total of 66. The null hypothesis will be rejected if 20 or more CRs are observed in 66 patients. This design yields a type I error rate of 0.05 and power of 90% when the true CRR is 0.4.

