9.7.1 Complete Response Rate

CRR will be defined as the proportion of patients with a best overall response (BOR) of CR, according to the 2014 Lugano classification ([Cheson et al., 2014](#)). The BOR will be derived based on response assessment performed on or before the start of subsequent anti-cancer therapy.

The percentage of CRR with its 95% confidence interval (CI) will be presented.

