### **Phase 2 Sample Size Calculation for the Cohort Where Loncastuximab Tesirine is Given at Every Cycle in Combination with Ibrutinib**

The primary hypothesis is that the CRR is based on central review for patients treated with the re-determined RP2D of loncastuximab tesirine and ibrutinib combination is significantly greater than 30% (i.e.,  $H_0: p \leq 0.3$  vs.  $H_a: p > 0.3$ ). This hypothesis will be tested at type I error of 0.05 (two sided).

A two-stage design with futility monitoring (Zeng et al., 2015) will be used. The null hypothesis that the true CRR is 0.3 will be tested against a one-sided alternative. In the first stage, 60 patients will be accrued. If there are 20 or fewer CRs in these 60 patients, this cohort will be stopped. Otherwise, 40 additional patients will be accrued for a total of 100. The null hypothesis will be rejected if 40 or more CRs are observed in 100 patients. This design yields a type I error rate of 0.05 and power of 85% when the true CRR is 0.45. Enrollment will continue during the interim analysis.

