### **5.9.1 Complete Response Rate**

CRR is defined as the proportion of patients with a best overall response (BOR) of complete response (CR). CRR is according to the 2014 Lugano classification (Cheson et al., 2014) as determined by the IRC (Phase 2 only) and the investigator (both Phase 1 and Phase 2).

The CRR and its 95% two-sided exact CIs will be presented by the IRC and the investigator, respectively.

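### Both Phase 2 two-stage designs are said to give a type I error of 0.05, but their one-sided rejection rules attain 0.024 and 0.020: a minor labelling error

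*SAP*

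**What the plan says.** SAP 4.1 and protocol 9.1.1 and 9.1.2 justify two single-arm, two-stage designs on complete response rate (CRR) by central review.

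- **Non-GCB, intermittent dosing.** The level is set first: "This hypothesis will be tested at type I error of 0.05 (two sided"). The next paragraph says "The null hypothesis that the true CRR is 0.2 will be tested against a one-sided alternative". The cohort stops at 5 or fewer CRs in the first 22 patients. Otherwise it goes on to 66, and "The null hypothesis will be rejected if 20 or more CRs are observed in 66 patients". The operating characteristics are then given: "This design yields a type I error rate of 0.05 and power of 90% when the true CRR is 0.4".
- **All DLBCL, every-cycle dosing.** The same two labels are used, with a null CRR of 0.3. The cohort stops at 20 or fewer CRs in 60 patients. Otherwise it goes on to 100, and "The null hypothesis will be rejected if 40 or more CRs are observed in 100 patients". The claim is "This design yields a type I error rate of 0.05 and power of 85% when the true CRR is 0.45".

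The protocol synopsis repeats the one-sided alternative and the 0.05 for both designs but omits the two-sided label. None of these places gives 0.025 or an attained error.

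The analysis sections plan estimation only. Protocol 9.7.1 says "The percentage of CRR with its 95% confidence interval (CI) will be presented", and SAP 5.9.1 says "The CRR and its 95% two-sided exact CIs will be presented by the IRC and the investigator, respectively".

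**The concern.** One test carries two labels. A rule that rejects only for many CRs has one tail, so its type I error is a single upper-tail probability at the null rate. If that probability is near 0.025, the sentence claiming 0.05 misstates the design, and only a two-sided nominal reading explains the figure. The synopsis does not offer that reading.

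Little is at stake. The error runs in the conservative direction, so it cannot inflate a false-positive claim. It does leave a wrong operating characteristic in the current design justification. A reader who checks the synopsis at one-sided 0.05, with the stated sizes and futility bounds, cannot explain why the cutoffs are 20 and 40.

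**Working it through.** **Inputs** (SAP 4.1; same figures in protocol 9.1.1, 9.1.2 and the synopsis)

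| | Non-GCB | Every-cycle |
|---|---|---|
| Stage 1 size n1 | 22 | 60 |
| Stop if CRs ≤ r1 | 5 | 20 |
| Total n | 66 | 100 |
| Reject if CRs ≥ r | 20 | 40 |
| Null rate p0 | 0.20 | 0.30 |
| Alternative p1 | 0.40 | 0.45 |
| Stated type I error | 0.05 | 0.05 |
| Stated power | 90% | 85% |

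**Formula.** With the futility stop followed,

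P(reject | p) = Σ over x1 from r1+1 to n1 of Bin(x1; n1, p) × P(X2 ≥ r − x1), where X2 ~ Bin(n − n1, p).

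Type I error is this sum at p0, and power is the sum at p1.

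**Step 1: the plan's power.** Non-GCB at p = 0.40 gives 0.904, and every-cycle at p = 0.45 gives 0.856. Both agree with the stated 90% and 85%, so the rules and the method are read correctly.

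**Step 2: the plan's type I error.** Non-GCB at p = 0.20 gives 0.0242, and every-cycle at p = 0.30 gives 0.0200. Neither is 0.05. The stated value is 0.05/0.0242 = 2.1 times and 0.05/0.0200 = 2.5 times the attained one. Doubling the attained values gives 2 × 0.0242 = 0.0484 and 2 × 0.0200 = 0.0400, which is how a two-sided nominal 0.05 would fit.

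**Step 3: is this only discreteness under 0.05?** Keep the sizes and futility bounds and move the final cutoff:

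| Non-GCB cutoff | Type I error | Power | Every-cycle cutoff | Type I error | Power |
|---|---|---|---|---|---|
| ≥18/66 | 0.0658 | 0.923 | ≥37/100 | 0.0679 | 0.932 |
| ≥19/66 | 0.0414 | 0.916 | ≥38/100 | 0.0474 | 0.915 |
| **≥20/66** | **0.0242** | **0.904** | ≥39/100 | 0.0315 | 0.890 |
| ≥21/66 | 0.0132 | 0.883 | **≥40/100** | **0.0200** | **0.856** |

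One-sided 0.05 is already held at 19 and 38. The plan's 20 and 40 are the smallest cutoffs that hold one-sided 0.025.

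**Step 4: Simon search for the non-GCB design.** Take p0 = 0.20, p1 = 0.40 and power 90%, with total sizes searched from 36 to 72. The optimal design (smallest expected size under the null) at one-sided 0.025 is exactly the plan's: 5/22, then reject at ≥20/66. Its probability of early stopping under the null is 0.7326, so its expected size is 22 + (1 − 0.7326) × 44 = 33.8. At one-sided 0.05 the optimum is a different design: 4/19, then reject at ≥16/54, with type I error 0.048.

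**Step 5: sensitivity to the futility stop.** If the stop were ignored, ≥20/66 gives 0.0306 and ≥40/100 gives 0.0210. Neither is 0.05.

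**The case against.** The strongest reply is that the qualifier is already in the text. In SAP 4.1 and protocol 9.1 the two-sided 0.05 stands in the paragraph just before, so the later 0.05 can be read as that nominal level, with 0.025 in the tested tail. On this reading it is a loose label, not a miscalculation. That is a likely account of how the figure arose, but it also means the tested tail is at 0.025. The sentence is still wrong for a test described as one-sided, its verb and the paired power describe attained values, and the synopsis lacks the qualifier.

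A second reply is that the cutoffs identify 0.025 only if the futility stop is binding. If the stop is ignored, 19/66 gives 0.0559, so 20 would be the smallest cutoff for one-sided 0.05. This is correct as arithmetic. However, the plan says a cohort at or below the bound is stopped, so the binding calculation applies. The dependence should be stated alongside the figure.

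Third, no document states 0.025, and SAP section 6 puts further details in separate documents that are not available here. For the every-cycle cohort the intended level is therefore an inference from its cutoff. The attained 0.0200 is not.

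Finally, nothing now depends on either rule. This is true, and it sets the grade.

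**Conclusion.** The stated type I error is wrong as written in both designs. The attained one-sided values are 0.024 (non-GCB) and 0.020 (every-cycle), against a stated 0.05, and the stated powers are right. The rules behave as one-sided 0.025 designs. The evidence for this is very strong for non-GCB, where the plan's design is the Simon optimum at that level. For every-cycle it rests on 40 being the smallest cutoff that holds 0.025. The figures assume that the futility stop is followed and that the planned 66 and 100 patients are reached.

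The point is minor. The error is conservative. SAP section 4 says the every-cycle cohort will not be enrolled, SAP 4.1 has the non-GCB cohort closing at 48 to 49 patients, and CRR will be reported with a confidence interval and no test.

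**What to change.** - In SAP 4.1 and protocol 9.1.1 and 9.1.2, replace the two-sided 0.05 level with a one-sided type I error of 0.025.
- In the same places and in the synopsis, replace the claimed 0.05 with the attained one-sided values: 0.024 for non-GCB and 0.020 for every-cycle. Say that these describe the planned 66- and 100-patient designs with the futility stop followed, so that 0.024 is not read as applying to the 48 to 49 patients treated.
- If the protocol is not amended again, record its correction in SAP 4.3, which at present lists no modifications.
- Add no rejection rule for the shortened non-GCB cohort. Report its CRR with the exact two-sided 95% interval already planned in SAP 5.9.1.

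The cost is wording only: one phrase and one figure per design. No patients, boundaries, data or analyses change.
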